Following an in-depth review of the literature, there are no human studies demonstrating use of Artesunate as a treatment for reducing multiple organ failure resulting from severe haemorrhage and injury. However, due to widespread use of Artesunate for the treatment of severe malaria, it has been available outside of the UK (and 'off-licence' inside the UK) in various non-GMP formulations (parenteral, oral, and rectal suppository) for a number of years. Therefore, there is a large volume of published information about clinical experiences with the drug, including in critically ill malaria patients. Collectively these studies have involved thousands of subjects. Several peer reviews have summarised various aspects of Artesunate trials, and have found Artesunate to be safe and well-tolerated (Riberio & Olliaro 1998, McIntosh & Olliaro 2000, Jones *et al.* 2007, Nosten & White 2007, Hess *et al.* 2010, Sinclair *et. al* 2012).

In a review of 188 (published and unpublished) trials, including 9241 subjects treated with Artesunate for malaria, Riberio & Olliaro (1998) found no serious adverse events or severe significant toxicity in a safety analysis of adverse events. In this review the most commonly reported adverse experiences were gastrointestinal symptoms. Occasional neutropenia (1.3%) reticulocytopenia (0.6%) and elevated liver enzymes (0.9%) were reported, and occasional instances of bradycardia/prolonged QT intervals (1.1%). Reports of neuropsychiatric disorders were reported in 4 patients on however they were all on con-current mefloquine.

McIntosh & Olliaro (2000) examined 41 trials of Artesunate in over 5000 patients and concluded that there was no evidence to suggest artemesinin drugs were more harmful than standard treatment for uncomplicated malaria. Similarly, Sinclair et al. (2012) examined 8 trials of Artesunate in severe malaria involving 1664 adults and 5765 children and reported no evidence of adverse effects of Artesunate, except for transiently worse neurological sequale in children.

Although artemisinins are recognized as a family of exceptionally safe drugs there have been four cases of IgE-mediated anaphylactic reactions to oral and intravenous Artesunate (Leonardi *et al.* 2001, Mohapatra *et al.* 2009, Dube *et al.* 2012). These allergic reactions to artemisinins are considerably rare.

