With respect to pregnancy, there are Cochrane database reviews of uncomplicated malaria treatment in pregnant women that discuss Artesunate (Orton & Garner 2005, Orton & Omari 2008). The current guidance suggests Artesunate may be given in the second and third trimesters for treatment of malaria, however due to insufficient evidence, it is not currently recommended for use in the first trimester unless benefits are considered to outweigh the risks (WHO, 2010).

With regards to the increased dose (4.8 mg/kg) we similarly do not expect significant adverse effect based on safety studies demonstrating that Artesunate can be safely administered up to doses of 8 mg/kg; Healthy volunteer Phase 1 studies have shown that single and multiple doses of intravenous Artesunate at the highest dose tested (8 mg/kg) were well tolerated with no serious side effects observed, and showed no dose-dependant increase in any adverse events, apart from a dose-related decrease in reticulocyte counts four days after dosing (Li *et al.* 2009, Miller *et al.* 2012).

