9.2 Assessment and management of risk

Artesunate has been extensively used in the treatment of both child and adult malaria including use in critically ill patients. They are very well tolerated, with a well-documented safety profile (see

previous section). As patients will receive all other clinically indicated treatments, there is no risk of ineffective therapy by administration of the trial treatment.

Whilst there is a risk of adverse events occurring as a result of oral or intravenous Artesunate, including gastrointestinal symptoms, neutropenia, reticulocytopenia, liver enzyme disturbance, bradycardia and prolonged QT intervals (Riberio & Olliaro 1998), these risks are low (all occurring in under 1.5% of recipients) and unlikely to result in significant detriment to the subject particularly in light of the serious nature of their injuries. Moreover, anaphylactic reactions to Artesunate are extremely rare.

The potential benefits of Artesunate in reducing multiple organ failure outweigh the risk of adverse events associated with the medication. Artesunate will be administered as an intravenous preparation due to the critical illness of the subjects enrolled that will preclude oral administration. Intravenous Artesunate has been more widely studied within the literature compared to intramuscular Artesunate (Jones *et al.* 2007) and is therefore the preferred route of administration in this trial.

This trial is categorised as: Phase 2a

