13.8 Trial Schedule

13.8.1 Schedule of Treatment for each visit

The following procedures will be conducted after arrival of the subject at the hospital.

Screening:

- Assess eligibility (refer to inclusion/exclusion criteria).
- Check that written agreement has been given to participate in the study in the form of a signed and witnessed informed consent form.
- Review medical and trauma history.
- Pregnancy test: by either urinary, serum, or point-of-care (see Fromm *et al.* 2012) testing of human chorionic gonadotrophin (hCG) for women of childbearing age.
- Vital signs (heart rate, blood pressure, respiration rate, oxygen saturations, body temperature, Glasgow Coma Score GCS).
- Dispense IMP in accordance with the randomization sequence.

Dosing:

• Body weight

- IMP administration
- Obtain blood samples for PK/PD analysis
- Monitor AEs and SAEs.

The following procedures will be conducted after dosing of the subject.

0 to 12 hours

- Blood sampling for PK/PD analysis
- Record baseline arterial blood gas.
- Monitor and record AEs and SAEs.
- Sequential organ failure assessment (SOFA) score.
- Renal injury, as per the risk, injury, failure, loss of function, endstage renal failure (RIFLE) score.
- Lung injury as per the Berlin definition.
- Infection rate.
- Number of ventilation free days.
- Renal Replacement Therapy (RRT) days.
- Vasopressors days.
- Composite time to complete organ failure (CTCOFR) score.
- Total length of critical care stay.
- Total length of hospital stay.

0 to 48 hours:

- Monitor and record AEs and SAEs.
- Record safety blood results.
- Record 24 hour fluid and transfusion requirements.
- Record concomitant medications.
- Sequential organ failure assessment (SOFA) score.
- Renal injury, as per the risk, injury, failure, loss of function, endstage renal failure (RIFLE) score.
- Lung injury as per the Berlin definition.
- Infection rate.
- Number of ventilation free days.
- Renal Replacement Therapy (RRT) days.
- Vasopressors days.
- Composite time to complete organ failure (CTCOFR) score.
- Total length of critical care stay.
- Total length of hospital stay.
- Record whether patient is alive and free of multiple organ failure (SOFA <5) at 48 hours

49 hours to Day 7:

- Monitor AEs and record SAEs.
- Record safety blood results.
- SOFA score.
- Renal injury, as per the RIFLE score.
- Lung injury as per the Berlin definition.
- Infection rate.
- Number of ventilation free days.
- RRT days.

- Vasopressors days.
- CTCOFR score.

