The total 60 mls of blood sampled equates to approximately 1% of the total circulating blood volume over the 12-hour period. As recruited patients will be receiving blood transfusions as part of their standard clinical care during this time, it is not anticipated that the samples taken will have any

adverse effects on clinical outcomes. Blood that is collected and not used for PK/PD analysis will be processed and stored for use in ancillary research (See Section 13.3.9)

Clinical Blood Sampling

In order to calculate SOFA and RIFLE scores, ascertain presence of infection, and degree of shock on admission, record will be made the following parameters as part of routine clinical bloods (i.e. no additional specific research blood draws will be taken):

- Platelets
- Creatinine
- Estimated Glomerular Filtration rate (eGFR)
- Bilirubin
- Total white blood cells
- Neutrophils
- Lymphocytes
- C-reactive protein
- Arterial or venous blood gas result (admission result only)

In addition, in order to ensure adequate safety of the IMP, the following will be monitored and for the purposes of safety monitoring for AEs and SAEs:

- Haemoglobin
- Haemocrit
- Red cell count
- Mean cell volume
- Mean corpulscular haemoglobin (MCH)
- Red blood cell distribution width (RDW)
- Mean corpuscular haemoglobin concentration (MCHC)
- White cell count
- Platelet count
- Neutrophils
- Lymphocytes
- Monocytes
- Eosinophils
- Basophils
- Alanine aminotransferase (ALT)
- Aspartate aminotransferase (AST)
- Alkaline phosphate
- Gamma-glutanyl transpeptidase (GGT),
- Bilirubin
- Creatinine
- Urea
- Sodium
- Potassium
- Calcium
- Albumin
- Prothrombin Time
- International Normalised Ratio (INR)

These parameters will be collected daily for days 1-7, and subsequently on day 14±1, day 21±1, and day 27±1, provided the subject is still in hospital. Where possible, these data will be collected from

routine clinical bloods. In the event they have not been undertaken as part of routine clinical bloods, the research fellow will take the bloods at the specified times (unless the subject declines).

Radiological Investigation Results

Radiological investigations (including Chest X-rays and CT scans) undertaken as part of a subjects' clinical course, will be examined for calculation of ARDS scores as well as for assessment of adverse events. No specific radiological investigations will be undertaken for research purposes.

Outcome Measures

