17.6 Adverse events that do not require reporting

The period for AE reporting is from dose administration to 28 days. The following SAEs are clinical outcome measures and are expected due to the nature of the injuries sustained:

- Deaths
- Infection
- Organ failure (single or multi-)
- Acute lung injury
- Acute kidney injury

The following SAEs are not clinical outcome measures but are expected SAEs due to the nature of injuries sustained:

- Thromboembolic events (deep vein thrombosis, pulmonary embolism)
- Ischaemic events (myocardial infarction, stroke, transient ischaemic attack)
- New-onset major bleeding

New onset major bleeding refers to a second episode of major bleeding which is temporally and clinically separate from the major haemorrhage that led to the entry of the participant into this study.

Any event meeting the definition of an SAE and not listed above will be treated as an 'unexpected SAE' and will require notification as outlined in Section 17.7.

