19.9 Interim analysis and criteria for the premature termination of the trial

An interim analysis will be performed after recruitment of the first 52 patients. The analysis will be limited to an analysis of safety data between the two groups. Provided there are no issues regarding safety or toxicity, the study will be continued with an increased dose in the intervention arm.

At the interim analysis, a qualitative assessment of all recorded AEs and SAEs will be undertaken by the DMC to determine if the trial should be discontinued on account of safety concerns. AEs will be coded by system organ class (SOC) and preferred term (PT), using MedDRA. An overview of all AEs, SAEs, relationship to IMP, intensity and AEs leading to withdrawals or death will be presented by treatment group. AEs will be summarised using descriptive statistics. Treatment emergent AEs will be analysed separately.

The number and percentage of subjects with abnormal vital signs and/or laboratory values will be presented by treatment group. The data may also be presented as shift tables (normal, abnormal and not clinically significant, abnormal and clinically significant) with screening values as a reference.

The trial will be terminated following the interim analysis based on the safety data. The criteria for termination (e.g. total SAEs per group) shall be defined by the DMC. Outside the planned interim analysis the study will be terminated only on the grounds of new safety concerns or unforeseen recruitment issues.

The sponsor retains the right to stop the study, should the need arise.

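### The one dose-dependent effect cited from the volunteer studies, a fall in reticulocytes four days after dosing, has no planned measurement; separately, Section 13.8.1 conflicts with other sections on recording non-serious AEs after 48 hours

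*Protocol*

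**What the plan says.** **Known effect.** Section 9.1 (Clinical Data) bases the higher dose on healthy-volunteer studies up to 8 mg/kg. They showed no dose-dependent increase in adverse events "apart from a dose-related decrease in reticulocyte counts four days after dosing". The same section summarises a review of malaria trials: "Occasional neutropenia (1.3%) reticulocytopenia (0.6%) and elevated liver enzymes (0.9%) were reported". Section 9.2 repeats the effect in its list of risks: "gastrointestinal symptoms, neutropenia, reticulocytopenia, liver enzyme disturbance, bradycardia and prolonged QT intervals".

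**What is measured.** Section 13.8.3 (Clinical Blood Sampling) states that "in order to ensure adequate safety of the IMP, the following will be monitored" and gives a list of tests. They are taken daily on days 1-7 and around days 14, 21 and 27 while the patient is in hospital. If routine care has not supplied a listed test, the research fellow draws the blood.

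**What is reviewed.** Section 19.9 provides that "a qualitative assessment of all recorded AEs and SAEs will be undertaken by the DMC", together with tables of abnormal laboratory values by group. Section 19.3 repeats the safety analysis on the final cohort.

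**AE recording.** In Section 13.8.1 the instruction up to 48 hours is to record both AEs and SAEs. From 49 hours to day 28 it becomes "Monitor AEs and record SAEs". Section 17.6 says: "The period for AE reporting is from dose administration to 28 days".

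**The concern.** Evaluating safety is a stated objective (Section 11.2), and the trial doubles the dose between its stages. The protocol identifies one effect that rose with dose in volunteers and gives its timing, yet leaves it off the list of tests that it fixes for safety. The trial could then report no dose-related haematological effect without having measured the one its own rationale names.

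The AE wording is a second and separate matter. What the DMC sees depends on what has been recorded, so sections that disagree about recording leave the content of its event tables uncertain.

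**Working it through.** No published figure underlies this point, so the check is mainly a comparison of sections.

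**1. Risks in Section 9.2 against tests in Section 13.8.3.** The safety list has 27 entries: seven haemoglobin or red-cell indices (haemoglobin, haematocrit, red cell count, MCV, MCH, RDW, MCHC), seven white-cell and platelet entries, five liver tests, six for renal function, electrolytes and albumin, and two for clotting (7 + 7 + 5 + 6 + 2 = 27). Of the blood effects named as risks:
- neutropenia (1.3% in the cited review): neutrophils are listed;
- liver enzyme disturbance (0.9%): ALT, AST, alkaline phosphatase and GGT are listed;
- reticulocytopenia (0.6%, and the only one described as dose-related): not listed.

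Planned reticulocyte values: 0 in 105 patients. Only a listed test triggers a research draw when routine care has not supplied it, so an unlisted count depends entirely on a clinician ordering it.

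**2. Timing.** Daily sampling on days 1-7 covers day 4. If the day of dosing counts as day 1, four days later is day 5, which is also covered. The gap is in the list, not the schedule.

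**3. Substitutes.** Entry requires active haemorrhage (Section 12.1), and Section 13.8.3 notes that patients will be receiving transfusions. Haemoglobin, red cell count, MCV and RDW will therefore reflect blood loss and donor cells, and cannot isolate a fall in reticulocytes.

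**4. Could AE reports fill the gap?** A reticulocyte fall is a laboratory finding, seen only if the count is run. Suppose every case were detected. The chance of at least one case in an arm of 35 at rate p is 1 - (1 - p)^35:
- p = 0.006 (the cited review): 1 - 0.994^35 = 0.19
- p = 0.05 (assumed): 1 - 0.95^35 = 0.83
- p = 0.10 (assumed): 1 - 0.90^35 = 0.975

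The rate in trauma patients is not given. At the cited rate an arm would probably show no case even with full detection, so case reports are a weak source. A scheduled count gives a value for every sampled patient, which can be compared between arms.

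**5. AE recording, section by section.**
- 13.8.1: recording of AEs and SAEs to 48 hours; afterwards AEs are monitored and only SAEs are said to be recorded.
- 11.6: AEs and SAEs reviewed daily for 28 days.
- 13.8.2: the grid marks AE and SAE monitoring identically to day 28.
- 13.8.4: fellows collect AEs and SAEs according to that grid.
- 17.4 and 17.7: a non-serious AE is recorded in the study file, with no 48-hour limit.
- 17.6: AE reporting to 28 days.

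Section 13.8.1 is out of line with the rest. It does separately call for safety blood results to be recorded from 49 hours to day 7, so a listed test at day 4 would be captured whatever the AE wording means. The two defects are independent.

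**The case against.** The strongest case for leaving the panel alone is that the protocol weighed this risk. Section 9.2 puts all the listed effects below 1.5% and considers them unlikely to cause significant harm. Section 9.1 gives neither the size nor the clinical consequence of the reticulocyte fall, and does not say whether single doses alone produced it. It reports a decrease at four days, not that this was the lowest point. Choosing a panel on that basis is partly judgement. That stands as a limit on how serious the omission is. It does not explain why two other effects from the same list are measured and the dose-related one is not.

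A second objection is that transfusion disturbs reticulocyte counts too. This also stands. Within a stage, randomisation gives a fair comparison with placebo. Between doses it does not, because the two doses are recruited in sequential stages (Sections 11.6 and 13.5.1).

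A reader might infer three stronger things, which the document does not support:
- *That the protocol as a whole stops recording non-serious AEs at 48 hours.* Sections 11.6, 13.8.4, 17.4, 17.6 and 17.7 keep them in scope to day 28 or without a time limit. The defect is a contradiction in 13.8.1.
- *That the dose-escalation review is blind to the dose relation because of this omission.* That review compares 2.4 mg/kg (n = 35) with placebo (n = 17) before anyone receives 4.8 mg/kg. Even with counts in hand it could show only a low-dose effect.
- *That the effect could never come to light, or that the safety endpoint fails.* A count ordered in routine care could be reported as an AE, and the formal safety endpoint is the 28-day SAE rate (Section 11.3.2), which an isolated laboratory fall would not normally enter.

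**Conclusion.** The point holds in this form: the trial has no planned, systematic measurement of the one dose-dependent effect that its volunteer evidence reports. No reticulocyte values are scheduled in 105 patients, and there would be none in the laboratory tables for the interim review (low dose against placebo only) or the final safety analysis. This cannot be left to the statistical analysis plan, since the protocol fixes what is collected. The omission is certain from the text. Its clinical weight is not, because the document does not give the size of the effect, and the judgement that red-cell indices are a poor substitute rests on the bleeding and transfusion the protocol describes. It is a gap worth an amendment, not a flaw that undermines the design.

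The AE wording in Section 13.8.1 is a separate internal contradiction that needs reconciling. It does not show that recording ends at 48 hours.

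**What to change.** 1. Add the reticulocyte count to the safety list in Section 13.8.3, on safety-blood days already scheduled and including day 4. Report it by arm in the Section 19.9 laboratory tables and in the final safety analysis. Read each dose mainly against the placebo patients of its own stage, and label any comparison between doses as non-concurrent. If the sponsor prefers to leave the test out, the protocol should say why.

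2. Reconcile Section 13.8.1 with Sections 11.6, 13.8.2, 13.8.4, 17.4, 17.6 and 17.7, so that one recording period for non-serious AEs applies throughout and the DMC knows what its event tables contain.

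**Cost.** One extra assay per chosen day, a CRF field and a short amendment, with no new sampling day. That the assay can be run on the existing blood-count sample is an assumption to confirm with the laboratory. Transfusion will make the values noisier. Item 2 is a wording change; it adds data entry only if the later period had been read as not requiring records.

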9.0 Introduction

9.1 Background

Multiple organ failure is common (30%) in the severely injured population and, if not fatal, results in worse outcomes such as prolonged critical care and hospital stays, and poor long-term quality of life. Development of multiple organ failure occurs early (within two days of admission) and correlates with an increase in nosocomial infections and if it persists, mortality (Minei *et al.* 2012). This figure rises rapidly as the degree of blood loss and shock intensifies. Patients requiring at least four units of red cell transfusions have longer critical care (9 vs. 5 days) and hospital stays (25 vs. 15 days). They also have a higher mortality (35% vs. 6%). Even modest improvements in these figures would have a significant improvement on patient experience, quality of life and the costs of healthcare.

Currently there are no specific treatments for organ failure. A therapeutic agent that reduces the incidence and severity of multiple organ failure could have a major global impact on the patient outcomes and resource utilisation.

The World Health Organisation (WHO) recommends intravenous Artesunate (a semi-synthetic artemisinin derived from the plant *Artemisia annua*) as the treatment of choice for severe malaria (WHO, 2010). Artesunate has very few adverse effects and the recommended intravenous bolus dose in adults/children with malaria is 2.4 mg/kg. Artesunate has been used by thousands of patients with malaria without important adverse effects (Sinclair *et al.* 2012). In man, Artesunate has a half-life of less than 30 mins and its active metabolite dihydroartemesinin (DHA) of less than 3 hrs. According to the WHO, the dose of Artesunate does not have to be adjusted in patients with renal failure or liver dysfunction.

In the first phase of the study, the dose of Artesunate (single bolus intravenous injection) proposed for administration to patients with trauma-haemorrhage is identical to the dose currently recommended by the WHO for the treatment of malaria (2.4 mg/kg), although in malaria Artesunate is repeatedly administered (every 12hrs), whilst in this study only one bolus dose will be injected. Thus, no significant adverse effects with Artesunate in patients with trauma-haemorrhage are expected. Provided the interim analysis demonstrates no safety concerns, the trial will proceed with the higher dose of Artesunate (4.8 mg/kg)—see also Section 9.2 for further safety data.

Pre-Clinical Data

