11.3.2 Secondary Endpoint

The secondary endpoints are:

- Maximum SOFA score: Maximum SOFA score over 7 days.
- Mean SOFA Score (Days 2-5).
- Prolonged organ failure: Defined as SOFA>5 on Day 7.
- Days on organ support: As per the CTCOFR score (Nadel *et al.*, 2007).
- Incidence of acute lung injury: As per Berlin definition (ARDS Task Force, 2012).
- Incidence of acute kidney injury: As per the RIFLE score (Bellomo *et al.*, 2004).
- Incidence of infection: As per definitions of infection by (Cole *et al.*, 2014).
- Number of ventilation free days.
- Total length of hospital stay.
- Total length of critical care stay.
- Mortality (discharge, 28 day and 90 day).
- Alive and free of multiple organ failure (defined as SOFA <=>) at 48 hours.

The safety endpoint is the serious adverse event rate in the first 28 days.

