Please see Appendix 2 for a full description of the outcome measures that will be recorded, including: SOFA Score, Renal injury (RIFLE Score), Lung Injury (ARDS Score), Infection rate, and days of organ failure (CTCOFR score).

Ventilator free days will be calculated by the subtracting the number of days spent on mechanical ventilation from 28.

Renal replacement therapy days will be calculated as the number of days spent on haemodialysis or haemofiltration.

Vasopressor days will be calculated as the number of days spent on ionotropic drugs, including for instance noradrenaline, dobutamine, vasopressin.

Length of stay will be recorded in days, for the total number spent in ACCU and in Hospital.

Mortality will be recorded at 28 days, discharge and 90 days.

At 48 hours it will be recorded whether the patient was alive and free of multiple organ failure (defined as SOFA≤5).

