19.6 Secondary outcome analysis

Secondary Outcome Analysis

The secondary endpoints that are continuous variables include: maximum SOFA score, mean SOFA Score (Days 2-5), number of days on organ support, number of ventilation-free days, number of days

in hospital, and number of days in critical care. Placebo and treatment groups will be analysed using appropriate standard tests of two-group comparison depending on data normality.

The secondary endpoints that are catagorical variables include: incidence of acute kidney injury as per the RIFLE classification. Secondary endpoints that are nominal variables include: incidence of prolonged organ failure, incidence of acute lung injury, incidence of infection, mortality rate (28-day, 90-day and discharge), and 'alive and free of multiple organ failure' at 48 hours. Placebo and treatment groups will be analysed using appropriate standard tests of two-group comparison.

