APPENDIX 2: SCORING SYSTEMS AND DEFINITIONS

PARAMETER	SCORE BREAKDOWN				
	0	1	2	3	4
PaO2/FiO2 ratio	>53.3	≤53.3	≤40	≤26.7	≤13.3
Platelets	≥150	<150	<100	<50	<20
Bilirubin	<20	20-32	33-101	102-204	>204
CVS	MAP	MAP<70	Dopamine ≤5	Dopamine >5 or	Dopamine >15 or
	≥70		or any dose	adrenaline ≤0.1 or	adrenaline >0.1 or
			dobutamine	noradrenaline	noradrenaline >0.1
				≤0.1 mcg/kg/min	mcg/kg/min
GCS	15	13-14	10-12	6-9	<6
Creatinine	≤109	110-170	171-299	300-440 or urine	>440 or urine
				<500ml/day	<200ml/day

1. SOFA Score Parameters (Vincent et al. 1998)

2. CTCOFR Scoring parameters (Nadel et al. 2007)

PARAMETER	DESCRIPTION	
Last day vasoactive agent	dobutamine <5 μg/kg/min or cessation of	
	adrenaline/noradrenaline/phenylephedrine or other	
	vasoactive agent	
Last day mechanical ventilation	IPPV, CPAP, Bimodal	
Last day renal replacement therapy:	peritoneal dialysis, haemodialysis, ultrafiltration,	
	haemofiltration	
For each parameter score 1 point per day up to 14 days		
Total CTCOFR Score if composite >14 days = 15 points		
Total CTCOFR Score if death during study (28 days) = 16 points.		

3. RIFLE Score Parameters (Bellomo et al. 2004)

	EGFR/SERUM CREATININE (Cr)	URINE OUTPUT
Risk	Cr x 1.5 or; eGFR decrease by >25% <0.5ml/kg/h for	
Injury	Cr x 2 or; eGFR decrease by >50%	<0.5ml/kg/h for 12 hours
Failure	Cr x 3 or; GFR decrease by >75% or; If baseline Cr	<0.3ml/kg/h for 24 hours
	>353.6 µmol/L, increase of 44 µmol/L	or; anuria for 12 hours
Loss of function	Complete loss of function >4 weeks	
End-stage kidney	Complete loss of function > 3 months	
disease		

4. Acute Lung Injury Definitions (ARDS Task Force, 2012)

THE BERLIN DEFINITION OF ACUTE RESPIRATORY DISTRESS SYNDROME		
TIming	<1 week of a known clinical insult or new or worsening respiratory symptoms	
Chest Imaging ^a	Bilateral opacities not fully explained by effusions, lobar/lung collapse,	
	nodules	
Origin of	Respiratory failure not fully explained by cardiac failure or fluid overload.	
Oedema	Need objective assessment (e.g. echocardiography) if no risk factor present.	
Oxygenation:		
Mild	200mmHg <pao2 cpapb ≥5 cmH2O</pao2>	
Mod	100mmHg <pao2 cmh2o<="" fio2="" peep="" td="" with="" ≤200mmhg="" ≥5=""></pao2>	
Severe	PaO2/FiO2 ≤100mmHg with PEEP ≥5 cmH2O	
a: Chest radiograph or Computed Tomography scan		
b: This may be delivered non-invasively in the mild acute respiratory distress syndrome		

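### Ventilator-free days are defined as 28 minus ventilated days, with no rule for death and no floor, so an early death can outscore a survivor who was ventilated longer

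*Protocol*

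**What the plan says.** - Section 11.3.2 lists "Number of ventilation free days" as a secondary endpoint, alongside hospital stay, critical care stay and mortality at discharge, 28 and 90 days.
- Section 13.8.3 gives the rule: "Ventilator free days will be calculated by the subtracting the number of days spent on mechanical ventilation from 28". It does not mention death, sets no minimum, and does not limit the ventilated days to the first 28. Sections 13.8.1 and 13.8.2 have ventilation recorded until discharge.
- On stay, the same section says only: "Length of stay will be recorded in days, for the total number spent in ACCU and in Hospital".
- Section 19.6 classes these outcomes as continuous (the list includes "number of days on organ support, number of ventilation-free days" and the two stay measures) and adds: "Placebo and treatment groups will be analysed using appropriate standard tests of two-group comparison depending on data normality".
- Appendix 2 handles death for CTCOFR, which is built from ventilation, vasoactive and renal support: "Total CTCOFR Score if death during study (28 days) = 16 points". A composite above 14 days scores 15, so no survivor can score as badly as a death.
- Patients who do not reach the 48-hour endpoint, for instance because they died, are replaced (13.9) and are not evaluable per protocol (19.12). The intention-to-treat population keeps everyone randomised (19.10).

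**The concern.** On this endpoint a higher value is meant to be better. Death ends ventilation, so under the written rule the days after death count as days free of the ventilator. An arm's mean then reflects how many patients died and how soon, and it can move in the wrong direction.

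This is a stated formula, so it cannot be treated as a detail left to the statistical analysis plan. A plan that scored deaths as 0 would depart from the protocol. The missing-data provision in 19.11 does not help either, because under this formula the value for a patient who died is not missing. Choosing a nonparametric test under 19.6 would rank the same faulty values.

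Section 19.1 says that the trial's data will inform whether to go on to a phase 2b study and how to design it. An endpoint that can improve because more patients died is a poor input to that decision.

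**Working it through.** The plan gives no figure for this endpoint, so there is none to reproduce.

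**Inputs from the protocol.** The constant 28 and the absence of a death term (13.8.3); the CTCOFR scores of 15 and 16 (Appendix 2). For patients given at least four red cell units, section 9.1 gives 35% mortality, a 9-day critical care stay and a 25-day hospital stay.

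**Assumptions.** Patients who die are ventilated until death on day *d*, from 3 to 7. Survivors are ventilated for *v* days, from 2 to 14. The protocol gives no ventilation duration, so the value of 9 borrows the critical care stay. Mortality *m* differs by 10 percentage points between arms, with *d* and *v* the same in both.

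**Step 1: two patients.**
- Ventilated until death on day 3: 28 - 3 = 25. CTCOFR = 16.
- Survivor ventilated for 9 days, with no longer vasoactive or renal support: 28 - 9 = 19. CTCOFR = 9.

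Ventilator-free days favour the patient who died by 6 days; CTCOFR favours the survivor.

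**Step 2: arm means, d = 3, v = 9, mortality 35% v 45%.**
- As written, mean = (1 - m)(28 - v) + m(28 - d):
  - 35%: 0.65 x 19 + 0.35 x 25 = 21.10
  - 45%: 0.55 x 19 + 0.45 x 25 = 21.70
  - The arm with more deaths looks 0.6 days better.
- Deaths scored 0, mean = (1 - m)(28 - v):
  - 35%: 0.65 x 19 = 12.35
  - 45%: 0.55 x 19 = 10.45
  - That arm is 1.9 days worse.

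**Step 3: the range.** The written mean simplifies to 28 - v + m(v - d). For 10 points more mortality the difference is therefore 0.10(v - d), whatever the baseline mortality. With deaths scored 0 it is -0.10(28 - v).

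| d | v | As written | Deaths scored 0 |
|---|---|---|---|
| 3 | 2 | -0.1 | -2.6 |
| 3 | 9 | +0.6 | -1.9 |
| 3 | 14 | +1.1 | -1.4 |
| 7 | 2 | -0.5 | -2.6 |
| 7 | 9 | +0.2 | -1.9 |
| 7 | 14 | +0.7 | -1.4 |

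Positive favours the arm with more deaths. The written rule does so exactly when v exceeds d.

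**Step 4: no floor.** A patient ventilated for, say, 30 days scores 28 - 30 = -2.

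**Step 5: stay.** If survivors stay 25 days and a death ends the stay on day *d*, mean stay is 25(1 - m) + dm. Ten points more mortality changes it by -0.10(25 - d), which is -2.2 days at d = 3 and -1.8 days at d = 7. A plain comparison could read that as benefit.

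**The case against.** The best defence is that little depends on this endpoint. It is one of about a dozen secondary endpoints in a phase 2a trial. The primary endpoint, the sample size and the safety endpoint are untouched. Mortality is reported at three time points, and CTCOFR already offers a measure that includes ventilation and penalises death. All of this stands. It lowers the severity, but it does not make the formula right.

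Three stronger readings are tempting, and the documents do not support them.

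- A reader might infer that the rule always rewards mortality, or that any early death beats any survivor. It does not. A survivor who was never ventilated scores 28, and when survivors come off the ventilator sooner than the others die, the written rule already counts against the arm with more deaths (the negative entries in the table). The 35% mortality is also a background figure, not shown to apply to deaths after 48 hours.
- A reader might illustrate the fault with a death on day 2, which would score 26. If that death falls before 48 hours, the patient is replaced and is not evaluable per protocol, so the example holds only in the intention-to-treat population. Later deaths remain in both populations.
- A reader might infer that length of stay has the same defect. For stay the protocol says what is recorded and is silent on deaths. It fixes no faulty formula, and the statistical analysis plan, which is not shown, could supply a rule.

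**Conclusion.** The point holds for ventilator-free days. The protocol fixes a formula that can place a patient who died above a survivor ventilated for longer, and that conflicts with how CTCOFR treats death. The fault covers deaths after 48 hours in both analysis populations, and all deaths under intention to treat.

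On the assumptions above, the written rule distorts the comparison enough to leave its sign uncertain, whereas scoring deaths as 0 gives a consistent direction. The ordering of individual patients follows from the formula alone. The size and direction of the difference between arms rest on the assumed day of death, ventilation duration and mortality difference.

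The stay measures are a secondary point about interpretation. Overall this should be fixed; since only secondary endpoints are involved, it does not undermine the trial's main comparison.

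**What to change.** In section 13.8.3, define ventilator-free days as the number of days alive and off mechanical ventilation from day 0 to day 28 (maximum 28), scored 0 for any patient who dies by day 28 and never below 0. State in section 19.6 that the arms are compared with a rank-based test.

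For critical care and hospital stay, keep the stated endpoints, but say that a shorter stay is not read as benefit without accounting for deaths, for example by ranking deaths as the longest stay.

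The cost is about one paragraph of text. No new data are needed for ventilator-free days, since 28-day mortality and ventilation days are already collected. The downside is that the endpoint becomes a composite with mortality, as CTCOFR already is, so a difference could come from survival, from ventilation, or from both. It should be read beside the separate mortality results.
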